## PROTOCOL AMENDMENT SUMMARY OF CHANGES TABLE

DOCUMENT HISTORY		
List dates of original protocol and all amendments in reverse chronological order.		
Document	Date	DNG Number
Amendment 1 (version 01)	19-MAR-2019	2018N385133_01
Original Protocol (version 00)	09-JAN-2019	2018N385133_00

### Amendment 1 19-MAR-2019

**Overall Rationale for the Amendment:** To amend the protocol with required changes from the Medicines and Healthcare products Regulatory Agency, UK

Section # and Name	Description of Change	Brief Rationale
3.3.1 Risk Assessment & 6.2 Exclusion Criteria	The exclusion criterion on renal function has been amended to an age appropriate GFR (CKD-EPI) of $\leq 90$ (ml/min/1.73m  ).  In alignment with this change, the mitigation strategy in the risk assessment table has also been updated.	MHRA requested changes to exclusion criterion.
6.2 Exclusion Criteria	An additional criterion has been added to exclude participants with abnormally low blood pressure, as determined by the Principal Investigator.	MHRA requested changes to add an additional exclusion criterion.
7.3 Measure to Minimize Bias: Randomization and Blinding	Additional wording has been added to include information on general and emergency unblinding.	To correct an omission in the original protocol, as identified by the MHRA.
8.1.2 Dose Escalation / Study Progression Stopping Criteria	One criterion has been updated to remove reference to two or more participants on active treatment experiencing the same / medically similar AE. This wording has now been updated to:  “Two or more participants in the same cohort experience a severe non-serious adverse reaction (i.e. severe non-serious adverse events considered as, at least, possibly related to the IMP administration), independent of within or not within the same system-organ-class.”	MHRA requested changes to the stopping criterion.

## 1. PROTOCOL SUMMARY

### 1.1. Synopsis

**Protocol Title:** A randomized, double-blind (sponsor unblinded), placebo-controlled, first time in human study to evaluate the safety, tolerability and pharmacokinetics of single (in both fed and fasted states) and repeat doses of GSK3186899 in healthy participants.

**Short Title:** Safety, tolerability and pharmacokinetics investigation of GSK3186899 in healthy participants.

**Rationale:** Visceral leishmaniasis (VL) is a parasitic disease caused by obligate intracellular protozoan parasites, particularly by the species *Leishmania donovani* and *Leishmania infantum/chagasi*. If left untreated, cases of VL are typically fatal. While therapies are available to treat the disease, none are ideal for use (due to toxicity, route of administration and cost) in resource poor settings where the disease is endemic. As such there is a real unmet medical need for new, short course oral drugs for the treatment of this disease.

The Phase 1 program will comprise a First Time in Human (FTIH) study of single and repeat ascending doses in healthy participants, incorporating a food effect component to investigate the influence of food on the pharmacokinetics (PK) of GSK3186899. The study will evaluate the safety, tolerability and PK profile of single and repeat ascending doses of GSK3186899. Results of this study are intended to be used to identify appropriate and well tolerated doses of GSK3186899 to be used in further studies. This study will be conducted at a single centre.

#### Objectives and Endpoints:

Objectives	Endpoints
Primary	

 
To evaluate the safety and tolerability of single and repeat doses of GSK3186899 in healthy participants
 
	
 
Adverse event reporting, clinical laboratory safety data, vital signs, 12 lead electrocardiogram (ECGs), 24 hours (hr) telemetry.
 

Secondary	
 
To evaluate the systemic PK profile of single (fasted and fed) and repeat doses of GSK3186899 in healthy participants
 
Plasma concentrations of GSK3186899 plus derived parameters, as data allow. For single ascending dose (SAD) part: Derived PK parameters for GSK3186899 following single dose (fasted and fed) including area under the plasma drug concentration versus time curve (AUC(0-t), AUC(0-∞), maximum observed plasma drug concentration (Cmax), time to maximum observed plasma drug concentration (Tmax), trough plasma concentration (Ctau) and
 

Objectives	Endpoints

 
• To examine dose proportionality following single and multiple doses of GSK3186899
 
• To assess accumulation and time-invariance ratios of GSK3186899 after multiple doses
 
	
apparent terminal half-life (<math>T_{1/2}</math>) as data allow. Predicted accumulation Ratio (<math>AR_{pred}</math>)# will be calculated.
 
For multiple ascending dose (MAD) part:  <math>AUC(0-t)</math>, <math>AUC(0-\infty)</math>, <math>AUC(0-\tau)</math>, <math>C_{max}</math>, <math>T_{max}</math> and <math>T_{1/2}</math>.
 
 
• Dose-proportionality assessment using derived PK parameters, as data allow:  For SAD part: <math>AUC(0-\infty)</math>, <math>C_{max}</math>  For MAD part: <math>AUC(0-\tau)</math>, <math>C_{max}</math>, <math>C_{\tau}</math>
 
• Accumulation ratios assessment*, where data allow: <math>RAUC(0-\tau)</math>, <math>RC_{max}</math>, <math>RC_{\tau}</math>. Time-invariance ratio calculation as <math>AUC(0-12)</math> on day 10 to <math>AUC(0-\infty)</math> on day 1.
 

Exploratory	

 
• To collect residual plasma following GSK3186899 analysis, and urine samples, for analysis of metabolites of GSK3186899
 
• To collect bile samples for analysis of metabolites of GSK3186899 (Part A Cohort 3 only)
 
	
 
• Metabolites of GSK3186899 in plasma and urine. These analyses will be run and reported separately from this protocol.
 
• Metabolites of GSK3186899 in bile. These analyses will be run and reported separately from this protocol.
 

\* Accumulation ratios calculated as the ratio of last dose to first dose PK parameters:  $RAUC_{(0-\tau)} = AUC_{(0-\tau)} \text{ on last dose to } AUC_{(0-\tau)} \text{ on first dose}$ ,  $RC_{max} = C_{max} \text{ on last dose to } C_{max} \text{ on first dose}$ ,  $RC_{\tau} = C_{\tau} \text{ on last dose to } C_{\tau} \text{ on first dose}$ . #  $AR_{pred} = 1/(1-e^{(k*\tau)})$  where  $k$  is elimination rate constant following the single dose and  $\tau$  is the dosing interval for the intended repeat dosing.

**Overall Design:** This study will be a randomized, double-blind (sponsor unblinded), placebo-controlled, 2-part study of the oral administration of GSK3186899 in healthy participants. As this will be the first time GSK3186899 is administered to humans, the study design may change based on emerging data as the study progresses.

This study is planned to include approximately 54 participants and will consist of 2 parts:

- Part A will include a single-ascending, sequential crossover design in up to 3 cohorts of participants (Cohorts 1, 2 and 3). Part A Cohorts 1-2 will comprise of a 4-way crossover which includes 4 dosing regimens under fasted conditions. Part A Cohort 3 will comprise of a 2-way crossover which includes 1 dosing regimen under fasted conditions and 1 regimen under fed conditions. The fed conditions regimen will investigate the effect on safety, tolerability and PK of a single dose of GSK3186899 following food administration.
- Part B will be a twice-daily (BID) 10-day repeat dose design in up to 3 parallel cohorts of participants (Cohorts 4, 5 and 6), although the dosing regimen may be altered depending on emerging data ([Appendix 5](#)). Part B may include drug administration after either fed or fasted conditions; this will be dependent on the interim results from Part A. If under fasted conditions, participants will be required to fast at least 2 hours before and after drug administration.

All participants in the study will attend a screening visit within 28 days prior to their first dose and a follow-up visit within 14-21 days after their final dose. If required, additional follow-up visits may be scheduled.

**Disclosure Statement:** This is a sequential cross-over (Part A) and parallel (Part B) treatment study with 6 arms that is participant and investigator blinded.

**Number of Participants:** A sufficient number of participants will be screened to ensure that a planned minimum of 54 are eligible to be randomized (Part A: 8 participants into each of Cohorts 1-2 and up to 14 participants for Cohort 3; Part B: 8 participants into each of Cohorts 4-6). A participant is considered evaluable if they complete both screening and at least one treatment period in Part A, or the 10-day treatment period in Part B. Participants that take part in Part A of the study cannot take part in Part B.

If participants prematurely discontinue the study, then additional replacement participants may be recruited and assigned to the same treatment sequence, at the discretion of the Sponsor in consultation with the Principal Investigator in both Parts A and B.

### **Treatment Groups and Duration:**

#### **Part A**

For the dose escalation phase in Part A, up to 3 cohorts may be used (Cohorts 1-3). Cohorts 1 and 2 will consist of 8 healthy participants each. Cohort 3 will consist of up to 14 healthy participants.

Cohorts 1 and 2 will each comprise of 4 treatment periods. Each participant will receive a maximum of 3 ascending oral doses of GSK3186899 and 1 placebo dose under fasted conditions. At each dose level, GSK3186899 and placebo will be administered in a 3:1 ratio, within each period, according to the randomization schedule in a blinded manner. Up to a maximum of 7 dose levels will be studied in Part A.

Cohort 3 will comprise of 2 treatment periods and investigate the effect of food on the safety, tolerability and PK of a single dose of GSK3186899, with a dose level (DLX)

previously selected from Cohorts 1-2. Dose selection will be based on in silico modelling, where the maximum exposure would not be exceeded following fed administration. The decision on the dose level of GSK3186899 to be administered will be made by the dose escalation committee (DEC). Each participant will receive a maximum of 2 oral doses of GSK3186899 under fasted and fed conditions. Bile samples will be collected under both fed and fasted conditions for the analysis of GSK3186899 and any metabolites.

### Study Duration of Cohorts 1-3

Screening	All screening assessments to be completed within 28 days prior to first-dose.
Treatment Period	Cohorts 1 and 2 will comprise of 4 treatment periods, investigating 4 dosing regimens under fasted conditions. Cohort 3 will comprise of 2 treatment periods, investigating 2 dosing regimens under fasted and fed conditions.  Each regimen will consist of a single dose given on Day 1, with participants in-house for 4 nights and 5 days. Participants will be admitted to the unit the day before dosing (Day -1) and will remain in the unit overnight until Day 4, when they will be discharged after completion of all assessments.
Washout Period	At least 10 days between each dose for an individual participant.
Follow-up	At least 14 days and no greater than 21 days after last study drug administration. If warranted, additional follow-up visits may be scheduled.
Total duration	Cohorts 1 and 2 will be approximately 11-12 weeks each Cohort 3 will be approximately 8-9 weeks

### Part B

For the repeat dose escalation phase in Part B, there will be up to 3 cohorts (Cohorts 4, 5 and 6), each cohort will consist of 8 healthy participants. Participants will only participate in one cohort. In each cohort, participants will be randomized to receive repeat doses of either GSK3186899 or placebo, administered in a 3:1 ratio according to the randomization schedule in a blinded manner. For BID dosing, GSK3186899 or placebo will be administered using a 12hr dosing interval. If another dosing regimen is selected for Part B based on emerging data, the interval between doses is outlined in [Appendix 5](#).

Participants will receive each dose after either fed or fasted conditions, dependent upon the interim results from Part A. If under fasted conditions, participants will be required to fast at least 2 hours before and after drug administration. Up to a maximum of 3 dose levels will be studied in Part B.

### Study Duration of Cohort 4-6

Screening	All screening assessments to be completed within 28 days prior to first-dose.
Treatment Period	Each Cohort will consist of a 10-day treatment duration (Days 1-10), with participants in-house for 14 nights and 15 days. Participants will be admitted to the unit the day before dosing (Day -2) and will remain in the unit overnight until Day 13, when they will be discharged after completion of all assessments.
Follow-up	At least 14 days and no greater than 21 days after last study drug administration. If warranted, additional follow-up visits may be scheduled.
Total duration	Approximately 8-9 weeks

**Data Monitoring Committee:** No

## 2. SCHEDULE OF ACTIVITIES (SOA)

Protocol waivers or exemptions are not allowed with the exception of immediate safety concerns. Therefore, adherence to the study design requirements, including those specified in the Schedule of Activities (SoA) tables (Section 2.1 and Section 2.2), are essential and required for study conduct.

Supplementary study conduct information not mandated to be present in this protocol is provided in the Study Reference Manual (SRM). The SRM will provide the site personnel with administrative and detailed technical information that does not impact participant safety.

This section lists the procedures and parameters of each planned study assessment. The exact timing of each assessment is listed in the SoA tables (Section 2.1 and Section 2.2).

The following points must be noted:

- If assessments are scheduled for the same nominal time, THEN the assessments should occur in the following order:
  1. 12-Lead ECG
  2. Vital Signs
  3. Blood Draws

Note: The timing of the assessments should allow the blood draw to occur at the exact nominal time.

- The timing and number of planned study assessments, including safety, pharmacokinetic, or other assessments may be altered during the course of the study based on newly available data (e.g. to obtain data closer to the time of peak plasma concentrations) to ensure appropriate monitoring.

- The change in timing or addition of time points for any planned study assessments must be documented in a Note to File, which is approved by the relevant GSK study team member and then archived in the study sponsor and site study files, but this will not constitute a protocol amendment.
- No more than 500 mL of blood will be collected over the duration of the study, including any extra assessments that may be required.
- The Institutional Review Board/Independent Ethics Committee (IRB/IEC) will be informed of any safety issues that require alteration of the safety monitoring scheme or amendment of the Informed Consent Form.

A table defining the allowed variance in timings of assessments without being considered a protocol deviation will be included in the SRM.

## 2.1. PART A (Cohorts 1-3)

Procedure	Screening (Up to 28 days before Day 1)	Study Period (Days)					Follow-Up (14-21 days post last dose) /Early Withdrawal	Notes
		-1	1	2	3	4		
Outpatient Visit	X						X	
Admission to Clinical Unit		X						
Inpatient Stay at Clinical Unit			←=====X=====→					
Discharge from Clinical Unit						X		Following completion of all assessments.
Informed Consent	X							
Inclusion and Exclusion Criteria	X							
Demography	X							
Full Physical Examination	X							Additional exams/screens may be performed, or brief exams can be made into full exams, by the Investigator, as deemed necessary (e.g. where safety or laboratory findings indicate). Tests will be conducted within site specified standards.
Brief Physical Examination		X		X		X	X	
Drug/Alcohol/Smoking Screen	X	X						Tests include alcohol breath test, smoking breath test and urine drug screen.
Medical/Medication/Drug/Alcohol History	X							
Human immunodeficiency virus (HIV), Hepatitis B and C Screening	X							
Follicle stimulating hormone (FSH) + Oestradiol	X							Females only, if required
Holter Monitoring (48 hours)	X							
Haematology/ Clinical Chemistry /Urinalysis Test (Include Liver Chemistries)	X	X		X		X	X	If trace protein in urine is detected, a repeat test can be performed (within 24 hours). If tests are considered abnormal, further quantification is required.  Non-fasted samples can be collected on Day -1 and the Follow-Up Visit. All other samples to be collected in a fasted state.
Urine Sampling (metabolism)			X	X				A urine sample will be taken pre-dose (approx. 20mL) All urine from each participant will be collected from 0-24 hrs post dosing. Details of urine collection and processing are described in the SRM.

Procedure	Screening (Up to 28 days before Day 1)	Study Period (Days)					Follow-Up (14-21 days post last dose) /Early Withdrawal	Notes
		-1	1	2	3	4		
Safety biomarkers (KIM1, NGAL, Urinary albumin)			X	X				
First urine sample of the morning to be collected (Day 1 sample collection should be pre-dose). Additional samples may be collected, as deemed necessary by the Investigator (e.g. where safety or laboratory findings indicate).

PK Blood Sampling			X	X				
PK blood samples to be taken pre-dose on Day 1 and then at the following time points post first-dose: 10min, 30min, 1hr, 1.5hr, 2hr, 2.5hr, 3hr, 4hr, 5hr, 6hr, 8hr, 10hr, 12hr, 24hr.
 
The time points stated may be modified depending on emerging SAD PK information as appropriate.
 
Blood volumes to be collected include 2 mL for all time-points from pre-dose to 10hrs, and 5 mL for time-points 12hr and 24 hr.

12-Lead ECG	X	X	T	X	↔X↔			
Vital signs to include heart rate (HR), blood pressure (BP), temperature and respiration rate. BP will be conducted in both a supine and standing position if participant develops any signs/symptoms which in the investigator's opinion are suggestive of adrenal insufficiency.
 
12-Lead ECG and Vital Signs to be conducted on Day -1 and pre-dose on Day 1 and then at the subsequent time points post-dose: 30 min, 1hr, 1.5hr, 2hr, 2.5hr, 4hr, 8hs, 12hr, 24hr, 48hr

Vital Signs	X	X	T	X	↔X↔	X		
Timings will be reviewed as cohorts progress and may be adjusted to ensure appropriate measurements relative to peak concentrations for subsequent cohorts.
 
T = Triplicate (for all assessments, except temperature and respiratory rate).
 
If any abnormal ECG reading is recorded, refer to Section 8.1.6 for appropriate action.

Procedure	Screening (Up to 28 days before Day 1)	Study Period (Days)					Follow-Up (14-21 days post last dose) /Early Withdrawal	Notes
		-1	1	2	3	4		
Telemetry			↔X→					Continuous at least 24hr post-dose. Initiate at least 15 min. prior to dosing.
Meals		X	X	X	X	X		
Fasting regimen: On Day 1, participants will have fasted 8hr overnight prior to dosing. An adapted standard breakfast will be served approximately 3hrs after dosing.
 
Fed regimen: On Day 1, participants will fast 8hr overnight and an adapted standard breakfast will be served approximately 30 mins prior to dosing.
 
Meals will be served as per the site schedule on Days -1, 2, 3 and 4.
 
Water permitted on an ad lib basis up to 1hr before dosing. No water to be taken in the hour prior to dosing except for the liquid part of the adapted standard breakfast for the Fed regimen. At least 8 fl oz (240ml) to be taken 1hr after dosing. No water to be taken in the hour after dosing except for the rinse of the dose.

Bile Sampling (Enteroto-test)			X					Cohort 3 only. Enteroto-test bile string swallowed 2hr post-dose, after 5hr the bile string will be removed.
Randomization			X					
Study Treatment			X					
Adverse event (AE) Review			↔=====X=====→			X		
Serious adverse event (SAE) Review	X		↔=====X=====→			X		
Concomitant Medication Review	X		↔=====X=====→			X		

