## 2.2. PART B (Cohorts 4-6)

Procedure	Screening (Up to 28 days before Day 1)	Study Period (Days)													Follow-up (14-21 days post last dose) / Early Withdrawal	Notes	
		-2	-1	1	2	3	4	5	6	7	8	9	10	11	12		
Outpatient Visit	X															X	
Admission to Clinical Unit		X															
Inpatient Stay at Clinical Unit			←-----X-----→														
Discharge from Clinical Unit																X	Following completion of all assessments.
Informed Consent	X																
Inclusion and Exclusion Criteria	X																
Demography	X																
Full Physical Examination	X																Additional exams/screens may be performed, or brief exams can be made into full exams, by the Investigator, as deemed necessary (e.g. where safety or laboratory findings indicate). Tests will be conducted within site specified standards.
Brief Physical Examination			X	X				X					X	X			
Drug/Alcohol/Smoki ng Screen	X		X														Tests include alcohol breath test, smoking breath test and urine drug screen.
Medical/Medication/ Drug/Alcohol History	X																
HIV, Hepatitis B and C Screening	X																
FSH + Oestradiol	X																Females only, if required
Holter Monitoring (48 hour)	X																

Procedure	Screening (Up to 28 days before Day 1)	Study Period (Days)													Follow-up (14-21 days post last dose) / Early Withdrawal	Notes		
		-2	-1	1	2	3	4	5	6	7	8	9	10	11	12	13		
Haematology/ Clinical Chemistry /Urinalysis Test	X		X		X		X		X		X		X		X		X	If trace protein is detected, a repeat test can be performed.  Sample to be drawn pre-dose on Days 2, 4, 6, 8 and 10.  Non-fasted samples can be collected on Day -1 and Follow-Up Visit. All other samples to be collected in fasted state.
Cortisol Test			X											X			Tests to be performed in the early morning on Day -1 and Day 11. If levels are <420 nmol/L, then a adrenocorticotropic hormone (ACTH) stimulation test will be performed to assess hypothalamic pituitary adrenal (HPA) axis.	
Safety biomarkers (KIM1, NGAL, Urinary albumin)				X				X									First urine sample of the morning to be collected (pre-dose). Additional samples may be collected, as deemed necessary by the Investigator (e.g. where safety or laboratory findings indicate).	
Telemetry				X	X												Continuous at least 24 hr post-evening dose. Initiate at least 15 min. prior to dosing.	
Randomization				X														

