### **8.1.3. Renal Withdrawal Criteria**

A participant that meets any of the following bulleted criteria will be withdrawn from the study:

- New onset of any clinically significant and persistent haematuria / proteinuria (Spot Urine Protein Creatinine (UPC) ratio  $>0.5$ ) in the absence of another clinical explanation e.g. calculus / infection. If trace proteins are detected, repeat test should be performed within 24 hours.
- If there is any change in serum creatinine  $> 26 \mu\text{mol/L}$  (0.3 mg/dl) from baseline or  $> 50\%$  from baseline. If change in serum creatinine measures at  $> 26 \mu\text{mol/L}$  (0.3 mg/dl), repeat within 24 hours. If confirmed, the participant will be withdrawn, and further investigations will be performed.
- Persistent hypophosphataemia (less than 0.8mmol/L) confirmed by repeat testing. If a participant meets the withdrawal criteria for hypophosphataemia, then further investigations will be performed.

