## NOTES :

1. Details of liver chemistry stopping criteria and required actions and follow-up assessments after liver stopping or monitoring event are given in Section 8.1.5. and [Appendix 6](#).
2. All events of ALT  $\geq 3 \times$  upper limit of normal (ULN) and bilirubin  $\geq 2 \times$  ULN ( $>35\%$  direct bilirubin) or ALT  $\geq 3 \times$  ULN and international normalized ratio (INR)  $>1.5$ , if INR measured, which may indicate severe liver injury (possible Hy's Law), must be reported as an SAE (excluding studies of hepatic impairment or cirrhosis).
3. Non-fasted samples can be collected on Day -1 and at the Follow-up visit (All Parts).
4. Safety biomarkers will be collected as urine samples.
5. Cortisol test will be performed in Part B only

Laboratory results that could unblind the study will not be reported to investigative sites or other blinded personnel until the study has been unblinded.

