5.2. Baseline Definitions

Baseline is defined as the last non-missing pre-dose assessment in each cohort. In general, assessments on Study day 1 taken prior to first dose are used as baseline. In some unlikely situations described below, the baseline will be defined as:

- when there are multiple assessments captured on Day 1, but the time of the first assessments is missing, then this first recorded assessment will be considered as the baseline
- when only one assessment is captured on Day 1 with time of assessment as missing, then conservatively the last available assessment from Day -1 or prior will be defined as the baseline
- when there are no assessments collected at Day 1, the last available data from either Day -1/ Day -2 or screening (as schedule of assessment in each Part/Cohort permits) will be defined as baseline
- when pre-dose data is completely missing for a subject, then no derivation will be performed, and the baseline will be set to missing

In Part A, for each period within a cohort, the period baseline is defined in a similar manner, by considering the last available non-missing pre-dose assessment in that period.

For some ECG and Vital Signs parameters, the pre-dose data is captured as triplicate. In these cases, the baseline will be defined as the mean of the assessments.

In addition, for some PK endpoint analyses, the adjusted baselines may be considered, if the pre-dose PK concentration value in a period is observed to be greater than 5% of the previous dose Cmax value:

- Subject level baseline is defined as the mean of baseline across periods for each subject. If a period baseline is missing, the mean of available period baselines will be considered as baseline.
- Period level baseline is defined as the difference between the baseline value and subject level baseline for each period and each subject.

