10.8.1. Laboratory Values

Haematology				
Laboratory Parameter	Units	Category	Clinical Concern Range	
			Low Flag (< x)	High Flag (>x)
Hematocrit	%	Male	<37	>50
		Female	<33	>45
		Δ from BL	N/A	> 7.5%
Hemoglobin	g/L	Male	<130	>170
		Female	<115	>155
		Δ from BL	N/A	> 30 g/L
Lymphocytes	x10 ⁹ /L		<1.2	>3.65
Neutrophils	x10 ⁹ /L		<2	>7.5
Monocytes	x10 ⁹ /L		<0.2	>1
Basophils	x10 ⁹ /L		<0.0	>0.1
Platelet Count	x10 ⁹ /L		<150	>400
White Blood Cell Count (WBC)	x10 ⁹ /L		<3.0	>10
Red Blood Cell Count (RBC)	x10 ¹² /L	Male	<4.4	>5.8
		Female	<3.95	>5.15

Clinical Chemistry				
Laboratory Parameter	Units	Category	Clinical Concern Range	
			Low Flag (< x)	High Flag (>x)
Albumin	g/L		< 34	> 50
Calcium	mmol/L		< 2.2	> 2.6
Creatinine	umol/L	Male	< 66	> 112
		Female	< 49	> 92
Glucose (Fasted)	mmol/L		< 3.9	> 5.8
Magnesium	mmol/L		< .6	> 1
Phosphate	mmol/L		< 0.87	> 1.45
Potassium	mmol/L		< 3.5	> 5.1
Sodium	mmol/L		< 135	> 145
Gamma GT	g/L		< 7.7	> 17.3

Liver Function				
Test Analyte	Units	Category	Clinical Concern Range	
			Low Flag (< x)	High Flag (>x)
Alkaline phosphatase	U/L	Female	< 35	> 104
		Male	< 40	> 129
AST/SGOT	U/L	Male	< 0	> 37
		Female	< 0	> 31
ALT/SGPT	U/L	Male	< 10	> 50
		Female	< 10	> 35
Total Bilirubin	µmol/L		< 0	> 20
Direct Bilirubin	µmol/L		< 0	> 20
Total Protein	g/L		< 63	> 83

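### The glucose baseline is the Day -1 sample, which may be non-fasted, while in-house post-dose samples must be fasted, so within-arm change from baseline can mix meal and drug effects

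*Protocol*

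**What the plan says.** Protocol 2.1 (Part A) schedules haematology, chemistry and urinalysis at screening, Day -1, Days 2 and 4, and Follow-Up. Protocol 2.2 (Part B) schedules them at screening, Day -1, Days 2, 4, 6, 8, 10 and 12, and Follow-Up, with the instruction "Sample to be drawn pre-dose on Days 2, 4, 6, 8 and 10". The Day 1 cell is empty in both tables.

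On fasting, Part A has "Non-fasted samples can be collected on Day -1 and the Follow-Up Visit. All other samples to be collected in a fasted state" and Part B has "Non-fasted samples can be collected on Day -1 and Follow-Up Visit. All other samples to be collected in fasted state". The notes to the laboratory table in Protocol Appendix 2 repeat the allowance for all parts.

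SAP 5.2 takes as baseline the last non-missing value before dosing. It adds a fallback: "when there are no assessments collected at Day 1, the last available data from either Day -1/ Day -2 or screening", as each schedule permits. Part A period baselines follow the same logic within each period.

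Protocol Table 7 specifies glucose as a fasted analyte. SAP 10.8.1 gives limits of potential clinical importance (PCI) of below 3.9 and above 5.8 mmol/L in a row that begins "Glucose (Fasted". SAP 10.12.5 plans chemistry change from baseline (Tables 3.9 and 3.10) and worst post-baseline PCI category relative to baseline (Tables 3.11 and 3.12).

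**The concern.** Glucose is treated as a fasted measurement and judged against fasted limits, but its reference value may be taken after food. If some Day -1 samples are non-fasted, the later fasted values will tend to be lower even when the drug does nothing, and Tables 3.9 and 3.10 would show an average fall. A raised non-fasted Day -1 value can also place a participant in the high category at baseline in Tables 3.11 and 3.12. A raised non-fasted Follow-Up value could become the worst post-baseline result.

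Clinical laboratory safety is part of the primary endpoint, and the planned summaries are descriptive and by treatment group, which is where such an artefact would appear. The informal interim analysis before Part B (SAP 3.1.1.2) lists participants from Cohorts 1 and 2 with any laboratory PCI value, without showing treatment. A non-fasted Day -1 glucose could trigger that listing, and no treatment comparison is available there to explain it.

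**Working it through.** The plan states no figure to reproduce. The check is a trace through the documents, followed by an illustration of size.

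**Trace**

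1. No chemistry is scheduled on Day 1 (Protocol 2.1 and 2.2). In the extracted text of the SAP's copy of the Part A schedule, a laboratory mark seems to fall on Day 1. The discharge mark in that copy also sits one column to the left of the protocol's, so this is a layout shift. The SAP's Part B copy agrees with the protocol.
2. SAP 5.2 says Day 1 values before dosing are generally the baseline. With none scheduled, the fallback applies and selects Day -1, which is later than screening.
3. Day -1 may be non-fasted. Days 2 and 4 (Part A) and Days 2 to 12 (Part B) must be fasted.
4. SAP 5.2, 5.2.1, 10.6 and 10.8.1 contain no rule on fasting status: no separate glucose baseline, and no exclusion of non-fasted values from Tables 3.9 to 3.12. Neither document says that fasting status is recorded.

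**Illustration (assumptions, not document values)**

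Let *q* be the share of Day -1 samples that are non-fasted and *d* the non-fasted minus fasted glucose difference in mmol/L. With no drug effect, the within-arm mean change to a fasted post-dose sample is -*q* × *d*:

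| *d* | *q* = 0 | *q* = 25% | *q* = 50% | *q* = 100% |
|---|---|---|---|---|
| 0.5 | 0 | -0.13 | -0.25 | -0.50 |
| 1.0 | 0 | -0.25 | -0.50 | -1.00 |
| 2.0 | 0 | -0.50 | -1.00 | -2.00 |

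The PCI limits are 5.8 - 3.9 = 1.9 mmol/L apart, so -0.50 is 0.50/1.9 = 26% of that width and -1.00 is 53%.

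*PCI category.* Assume fasting glucose is normal with mean 4.85 (the midpoint of 3.9 and 5.8) and SD 0.4. The chance that one value exceeds 5.8 is 1 - Φ((5.8 - 4.85 - *d*)/0.4). This is about 1% when fasted, 13% at *d* = 0.5 and 55% at *d* = 1.0. The same figures apply to a non-fasted Follow-Up value.

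*Placebo contrast.* If *q* is the same in both groups, the expected active-minus-placebo difference is -*qd* - (-*qd*) = 0. The SD of chance imbalance is *d* × √(*q*(1 - *q*)) × √(1/n₁ + 1/n₂), treating fasting state as independent between samples. With *q* = 50% and *d* = 1.0:

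- Part B, one dose group of 6 against pooled placebo of 3 × 2 = 6: 0.5 × √(1/6 + 1/6) = 0.29 mmol/L.
- Part A, 6 against pooled placebo of at most 16 (one placebo dose for each of 16 participants): 0.5 × √(1/6 + 1/16) = 0.24 mmol/L.
- Without pooling, 6 against 2: 0.5 × √(1/6 + 1/2) = 0.41 mmol/L.

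If the baseline sample is fasted, *q* = 0 and all these terms vanish.

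**The case against.** The strongest reply is that the protocol permits non-fasted Day -1 samples and does not require them. In Part B participants are in-house from Day -2 and already have an early-morning Day -1 draw for cortisol, so the chemistry sample may be fasted in practice. This stands. A reader might infer a shift in the same direction in every participant, but the documents do not support that: zero is a possible value.

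Second, placebo participants follow the same rule. A reader might infer that two placebo participants per cohort are too few to help. SAP 5.1, however, pools placebo within each part for display, and the contrast is unbiased in expectation when the non-fasted share is equal. This also stands for Cohorts 1, 2 and 4 to 6, at the price of added noise. It does not help Cohort 3, which has no placebo, or anyone reading a within-arm change.

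Third, the SAP does not say that the fasted limits apply to every sample, and the programming standards may treat non-fasted values separately. That is fair. The point is that the SAP is silent, so the outcome depends on programming that the plan does not specify.

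Fourth, no hypothesis is tested, and a screening sample, which the same rule requires to be fasted, exists as a reference. Both are true. They limit the consequence, but SAP 5.2 would not select the screening value while a Day -1 value is present.

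**Conclusion.** The mismatch is real for glucose. It affects within-arm change from baseline and baseline PCI category, and it leaves open whether a non-fasted Follow-Up value counts as the worst post-baseline result. Its size lies between zero and the full meal effect. The documents give neither the non-fasted share nor the meal effect, so the figures above are illustrations. The consequence is modest, because the tables are descriptive and placebo offers an unbiased if noisier contrast outside Cohort 3. It still merits correction: it touches a primary-endpoint summary and the remedy is cheap.

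A reader might extend the point to the renal withdrawal criterion in Protocol 8.1.3, which begins "If there is any change in serum creatinine". The documents do not support that step. Section 8.1.3 refers to a baseline without defining it, the SAP definition is written for analysis, and nothing in either document marks creatinine as meal-dependent. The urinary kidney biomarkers (KIM-1, NGAL, albumin) use first-morning samples, pre-dose on Day 1, and are untouched.

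**What to change.** - **Part B:** draw the Day -1 chemistry sample fasted, together with the early-morning cortisol sample, and delete the Day -1 non-fasted allowance from Protocol 2.2 and the matching Appendix 2 note. No extra sample is needed.
- **Part A:** add one chemistry tube on Day 1 before dosing, after the 8-hour overnight fast already required, and use it as the period baseline. SAP 5.2 would then select it without rewording. In the Cohort 3 fed period, state that the tube is drawn before breakfast. Breakfast starts about 30 minutes before dosing, and the documents do not place the pre-dose draw ahead of it.
- **SAP:** keep non-fasted glucose (Follow-Up, and any Day -1 value not recorded as fasted) out of Tables 3.9 to 3.12 and list it only. If sampling cannot change, this rule alone would protect the glucose tables, with the fasted screening value as a possible glucose baseline.

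**Cost:** one small tube per Part A period at an existing pre-dose draw, taken slightly earlier in the fed period. That is up to four tubes per participant in Cohorts 1 and 2 and two in Cohort 3, to be counted within the 500 mL limit. Fasting status must also be recorded for each chemistry sample, because the exclusion rule cannot be programmed without it.
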